Weight Loss and Exercise To Improve Rheumatoid Arthritis Cardiovascular Risk

SWET vs CHAT Study

NCT04356183

Document Date: 01/18/2024

Purpose of the Study

Aim 1: To determine if, compared to a counseling health as treatment (CHAT) program consistent with current standard of care, a 16-week supervised weight loss and exercise training (SWET) program improves cardiovascular risk in older, obese persons with RA.

Hypothesis 1a: Compared to CHAT, SWET produces superior improvements in metabolic syndrome (MSSc).

Hypothesis 1b: Compared to CHAT, SWET produces superior improvements in systemic inflammation, RA disease activity and monocyte/macrophage function.

Twenty-six older (ages 60-80 yr.), obese (BMI 28-40 kg/m²) persons with RA (seropositive or erosive) will be randomized to 16 weeks of CHAT or SWET. CHAT is a control arm based on traditional clinical counselling. SWET includes aerobic (3x/w) and resistance (2x/w) training plus a weekly weight loss session. At baseline and post-intervention, comprehensive assessments of “traditional” CV risk will include anthropometrics, blood pressure, body composition, cardiopulmonary exercise tests, and fasting blood for glucose, insulin and lipoprotein profiles. “Inflammatory” CV risk measures will include systemic inflammatory markers, disease activity (DAS-28) and monocyte/macrophage function.

The primary outcome variable is change in a highly validated, continuous z-score for metabolic syndrome (MSSc); MSSc are derived using participants' blood pressure, waist circumference, HDL-cholesterol, triglycerides, and glucose normalized to recommended threshold normative values. With 20 (accounting for 25% attrition) persons total completing both arms, we have 80% power (one-sided) to detect a difference in MSSc change of 1.8 ± 2.1 , where each unit difference in MSSc corresponds to a HR for CV disease of 1.49 (CI 1.37, 1.62).

Aim 2: To determine if, compared to a CHAT program consistent with current standard of care, a 16-week SWET program improves patient-reported outcomes in older, obese persons with RA.

Hypothesis 2: Compared to CHAT, SWET produces superior improvements in self-reported global health, pain, fatigue, and physical function.

Baseline and post-intervention, global health, pain, fatigue, and physical function will be assessed using highly validated measures from the Patient Reported Outcomes Measurement System (PROMIS).

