These data show that relative to a Control group with little change in MSSc, aerobic training and weight loss improve MSSc by -2.5 ± 2.1 . Based on these we would expect similar improvements in our supervised intervention arm (SWET) that includes each of aerobic training, weight loss, and resistance training. Yet, because the SWET 16 week intervention period is on the shorter end of the 16-24 week STRRIDE interventions, full improvements may not be completely achieved. To detect a significant difference between SWET and, the counseling control arm (CHAT) of 1.8, assuming a standard deviation for change of 2.1, 20 persons total will deliver 80% power with a one-tailed alpha of 0.05. We justify a one-tailed test based on our hypothesis that the SWET will significantly exceed CHAT for metabolic syndrome score reduction and that CHAT exceeding SWET, is implausible. Based on our prior experience, we expect an attrition rate of 25% during the intervention period, randomizing a total of 26 RA participants to achieve 20 participants completing the intervention.

Statistical Methods: To assess the difference between SWET and CHAT with respect to the primary and secondary outcomes, we will create change scores (Post-intervention – Pre-intervention) and use linear

models to assess group differences. Distributions will be assessed, and nonparametric methods used or transformations performed if the distribution of the outcomes are non-normal. We will control for important baseline variables, including baseline levels of the outcome of interest. Non-adherent individuals, including those failing to complete the intervention, will be analyzed as specified under an intention-to-treat criterion. Statistical significance will be established as $P<0.05$ (one-tailed) for the primary outcome, MSSc.

Secondary and exploratory outcomes will be tested at $P<0.05$ without Type-I error control for multiple outcomes. When results are reported, we will alert the reader of the P-value issues inherent in the testing multiple of multiple outcomes. This rich database can be used for exploratory analyses, including mediation, moderation, and mechanism; examples include (a) if level of compliance impacts level of change in the CV measures, (b) if change in one CV measure impacts change in other measures (possibly irrespective of group), and (c) interactions. The analyses will proceed chronologically in 4 phases.

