Descriptive analyses that will summarize the distribution of the covariates and dependent variables. Bivariate analyses of the association between group membership and the outcome measures. Controlled multivariable analyses, which assess the association between intervention arm and the outcomes controlling for the important covariates – prespecified prior to analysis (see below). Controlled multivariable analyses, which assess the association between outcomes and potential mediators controlling for the important covariates.

Correlation of all outcome changes, which will assess if the intervention has a generalized change across all outcomes, or, is specific to varying outcomes depending on the person. This exploratory analyses may lead to models that predict what kind of person changes in this area but not some other area. While we recognize we have limited power for these exploratory analyses, they may lead to future investigations of individualized prescriptions for weight loss and exercise for certain outcomes. Inclusion of covariates, such as the baseline measure for the outcome of interest, into the models will add precision to the estimates and allow us to assess the generalizability of the effects across the covariates. The list of covariates (i.e. age, race, gender, BMI, disease activity) will be developed prior to any analysis.

Handling of “dropouts”: In addition to intention-to-treat analyses described above, rates of non-adherence and lack of completion will be assessed. The sample that completed versus those that did not will be compared with respect to demographic and clinical differences. These analyses will help improve adherence in future studies as well as to determine any potential impact of dropouts on the findings.

Handling of missing data from participants completing the intervention: Every effort will be made to ensure complete data on all participants. However, occasions arise (e.g. unable to obtain sufficient blood for monocyte functional analyses) where data will be unavailable. Missing data will be assessed for whether it is missing at random, missing completely at random, or missing not at random. For the first two, pair-wise deletion of missing data (If the post-intervention value is missing, the pre-intervention value will be deleted.) will be performed prior to analyses of group differences. If missing

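### A correlation of person-level outcome changes cannot show that SWET produces generalized change; that question needs the SWET–CHAT comparisons (minor, exploratory analysis only)

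*Combined protocol and SAP*

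**What the plan says.** The analysis is in the combined protocol and SAP, section Data Analysis & Statistical Considerations, in the list of analysis phases under Statistical Methods. The entry reads "Correlation of all outcome changes, which will assess if the intervention has a generalized change across all outcomes, or, is specific to varying outcomes"; the last clause, in full, is "is specific to varying outcomes depending on the person". The text then says that this work may suggest which kinds of people change in one area but not another, and may prompt later studies of individualized weight-loss and exercise prescriptions. It labels the work exploratory and concedes that "we recognize we have limited power for these exploratory analyses".

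The quantities correlated are each person's post-minus-pre changes, defined earlier under Statistical Methods. The plan does not say whether the correlations are pooled, within arm or adjusted for arm. It gives no test or threshold for them and no rule for attributing them to the intervention. The nearest related example, in the same section, is "if change in one CV measure impacts change in other measures (possibly irrespective of group").

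Arm comparisons for each outcome are planned separately, as linear models on change and as "Bivariate analyses of the association between group membership and the outcome measures". The plan does not link them to the generalized-or-specific question.

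**The concern.** The sentence asks what the intervention does, and answers with a statistic about how two changes vary together between people. These are different quantities. Changes in pain, fatigue, function and global health may well move together in people who receive no effective intervention, for example through flares, mood or response style. A positive correlation could then be read as a generalized SWET effect when there is none. Conversely, a benefit that is the same for everyone leaves no trace in a within-arm correlation.

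The stake is limited but real. The plan intends this result to inform future work on individualized prescriptions, and producing input for later trials is a stated purpose of the study. A misread correlation could therefore reach the next design.

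**Working it through.** The plan gives no figure for this step, so there is none to reproduce.

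**Inputs**
- Effect size: Expected Effect Size and Power sets a between-arm difference "of 1.8, assuming a standard deviation for change of 2.1", so d = 1.8/2.1 = 0.857 SD. Those figures are for the metabolic syndrome score (MSSc); using them for other outcomes is an illustration.
- Sample size: 20 completers, from the same section. Allocation is not stated; 1:1 is assumed, giving 10 per arm.
- Within-arm (natural) correlation of two changes, r_w: not in the documents. Assumed, over a range.
- Test: two-sided 0.05, assumed. The critical correlation at n = 20 is 0.444.

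**Step 1: within arm or adjusted for arm.** Adding a constant to every change score in an arm does not alter the correlation in that arm. For a uniform SWET benefit of any size the expected value stays at about r_w. This is algebra and needs no assumed input.

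**Step 2: pooled over arms.** With 1:1 allocation and arm differences d1 and d2 in SD units,

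r_pooled = (r_w + d1·d2/4) / √[(1 + d1²/4)(1 + d2²/4)].

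At d = 0.857, d²/4 = 0.184.
- No effect: r_pooled = r_w.
- One of two outcomes shifted, r_w = 0.5: 0.5/√1.184 = 0.46.
- Both shifted, r_w = 0.5: (0.5 + 0.184)/1.184 = 0.58.
- Both shifted, r_w = 0: 0.184/1.184 = 0.155, well below 0.444.
- Both shifted by 3 SD, r_w = 0: 2.25/3.25 = 0.69.
- A pooled value of exactly zero at d = 0.857 in both needs r_w = −0.18.

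**Step 3: how often the correlation is significant.** Simulation of bivariate normal changes, 10 per arm, 40,000 trials per case:

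| True situation, r_w = 0.5 | Pooled | Adjusted for arm |
|---|---|---|
| SWET affects neither outcome | 64% | 62% |
| SWET shifts one outcome by 0.857 SD | 55% | 62% |
| SWET shifts both by 0.857 SD | 81% | 62% |

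With no effect and r_w = 0.3 or 0.6, the pooled rates are 25% and 84%, and the arm-adjusted rates 24% and about 81%. With both outcomes shifted by 0.857 SD and r_w = 0, the rates are 10% pooled and 5% adjusted, the latter being the null rate.

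The arm-adjusted correlation does not distinguish the three situations. The pooled one responds to them, but in the wrong order: a benefit on one outcome lowers it below its value with no benefit at all. Its level is set mainly by r_w, which is unknown.

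**The case against.** **The pooled correlation does respond to SWET.** This stands. A reader might infer that the correlation is zero whenever SWET helps everyone, or that the conclusion would never depend on whether SWET works. The documents do not support either, because they leave the pooled option open and a large uniform benefit gives a strong pooled correlation (0.69 at 3 SD). The zero holds only within arm or adjusted for arm, and then only if the natural correlation is zero.

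**The sentence is about persons.** It ends "is specific to varying outcomes depending on the person". For whether the same people change on several outcomes, correlation is a reasonable description. That stands too. It does not rescue the first half of the sentence, whose subject is the intervention.

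**No decision rule is stated.** Correct. The percentages above rest on a test and on natural correlations supplied for illustration. The invariance in Step 1 does not.

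**The analysis is exploratory and the arm comparisons are already planned.** Both are true, and they keep the point minor. The limited-power caveat concerns precision, however, and more people would not help: with no effect and r_w = 0.5, moving from 20 to 26 people raises the pooled rate from 64% to 77%.

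**A global test might seem the natural replacement.** It does not separate generalized from specific effects. With four independent outcomes, shifting two by 1.714 SD or all four by 0.857 SD gives the same mean shift (2 × 1.714/4 = 0.857), and so the same power.

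**Conclusion.** The concern holds as a minor point about one exploratory analysis. A correlation of person-level changes cannot attribute generalized change to SWET. Within arm or adjusted for arm it carries no information about a uniform benefit; pooled, it mixes that benefit with natural co-variation. At an assumed natural correlation of 0.5, a significant pooled correlation is about as likely with no effect (64%) as with an effect on one of two outcomes (55%), and only moderately more likely with an effect on both (81%).

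The rates depend on 1:1 allocation, normal changes, the assumed correlations and a test that the plan does not state. The mismatch between question and statistic does not depend on them.

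A reader might infer that the patient-reported hypothesis, "Compared to CHAT, SWET produces superior improvements in self-reported global health, pain, fatigue, and physical function", is compromised. It is not: it is tested by comparing arms. The primary MSSc comparison is likewise unaffected.

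**What to change.** Reword the entry so that:
- The generalized-or-specific question is answered from the SWET–CHAT comparisons already planned. Show them side by side as standardized differences with intervals, signed so that improvement points the same way, for outcomes that share no components (MSSc should not sit beside its own ingredients).
- Correlations of change are reported separately for SWET and CHAT, as description of who changes together, and are not attributed to the intervention.
- The text states that about 10 people per arm cannot settle person-specific response. At n = 10, the 95% interval around a correlation of zero runs from about −0.63 to 0.63.

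A SWET–CHAT comparison of the average standardized change is optional and should be labelled a test of overall effect. For four outcomes each shifted by 0.857 SD (two-sided 0.05, 10 per arm), its power is 95%, 75% or 63% if the outcomes correlate 0, 0.3 or 0.5. The lower figures are the relevant ones if the changes move together.

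The cost is one reworded paragraph and a standardization of results from data already collected. The side-by-side estimates will themselves be imprecise: the standard error of an unadjusted standardized difference is about √(1/10 + 1/10) = 0.45, so each interval is roughly ±0.9 SD. The downside is that the claim about individualized response becomes more modest.

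### Would adding all five named covariates to baseline MSSc cost the primary comparison precision?

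*Combined protocol and SAP*

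**What the plan says.** All of this is in the combined protocol and SAP, under Data Analysis & Statistical Considerations.

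- Statistical Methods sets out linear models on change scores: "We will control for important baseline variables, including baseline levels of the outcome of interest". The baseline outcome is the only covariate named there.
- The list of analysis phases that follows has a bivariate arm comparison and then "Controlled multivariable analyses, which assess the association between intervention arm and the outcomes controlling for the important covariates". That item says the covariates are prespecified and points forward to a later list.
- The later list reads: "The list of covariates (i.e. age, race, gender, BMI, disease activity) will be developed prior to any analysis".
- The sentence just before it gives two purposes for covariates: "Inclusion of covariates, such as the baseline measure for the outcome of interest, into the models will add precision to the estimates", and to "allow us to assess the generalizability of the effects across the covariates".
- Expected Effect Size and Power states that "20 persons total will deliver 80% power with a one-tailed alpha of 0.05". The calculation uses a difference of 1.8 and an SD of change of 2.1, and takes no credit for covariates.
- On the analysis set: "Non-adherent individuals, including those failing to complete the intervention, will be analyzed as specified under an intention-to-treat criterion". The sample behind the primary test therefore lies between 20 completers and all 26 randomised.

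**The concern.** The precision statement carries no condition. It is reasonable for the baseline value of the outcome, which usually predicts change. It is less safe for five further variables in a trial this small. Each term uses a residual degree of freedom, and in a small sample it also picks up chance correlation with arm, which inflates the variance of the arm effect. Unless the covariates predict MSSc change well enough to offset this, the adjusted estimate is less precise than one adjusted for baseline alone.

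The phase list can fairly be read as putting all five into the arm comparison. The documents give no R-squared and no count of model terms, and they do not say whether the bivariate or the controlled comparison carries the one-tailed primary test. What would be at stake is power for the single primary comparison. The validity of that test is not in question.

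**Working it through.** **Inputs from the document.** Difference 1.8, SD of change 2.1, one-tailed alpha 0.05, 20 completers, 26 randomised, five named covariates plus baseline MSSc.

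**Assumptions.** 1:1 allocation (no ratio is stated); one model term per covariate; covariates unrelated to arm because of randomisation. Every R-squared is assumed. The n=26 figures need an outcome for everyone randomised, so they are an upper bound.

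**1. The plan's own figure.** With 10 per arm the unadjusted SE is 2.1 × √(2/10) = 0.939, and the noncentral t gives one-sided power of 57.9%, against the stated 80%. With 13 per arm the SE is 2.1 × √(2/13) = 0.824 and power is 68.4%. This shortfall is a separate matter. The break-even points in step 3 depend only on n and the number of terms.

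**2. Cost of covariates.** With k covariates in the model, the expected variance of the arm effect is multiplied by (n−3)/(n−3−k) before any prognostic gain.

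- n=20: baseline only 17/16 = 1.0625; all six 17/11 = 1.545.
- n=26: baseline only 23/22 = 1.045; all six 23/17 = 1.353.

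**3. Break-even for j extras over baseline alone.** The variance ratio is (n−4)/(n−4−j), so the extras must explain more than j/(n−4) of the variance left after baseline.

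| Extras | n=20 | n=26 |
|---|---|---|
| 1 | 1/16 = 6% | 1/22 = 5% |
| 2 | 2/16 = 13% | 2/22 = 9% |
| 5 | 5/16 = 31% | 5/22 = 23% |
| 6 (race as two terms) | 6/16 = 38% | 6/22 = 27% |

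Baseline MSSc alone, against no adjustment, needs 1/17 = 6% or 1/23 = 4%. If five extras explain nothing, the SE rises by √(16/11) − 1 = 21% at n=20 or √(22/17) − 1 = 14% at n=26. Judged on interval width, which also counts the larger t critical value, the five-extra thresholds are about 34.5% and 24.5%.

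**4. Effect on power**, with baseline MSSc assumed to explain 20% of change variance. Power is averaged over simulated designs.

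| Model | n=20 | n=26 |
|---|---|---|
| Baseline only | 64% | 75% |
| Five extras explaining 0% of the remainder | 51% | 65% |
| 10% | 54% | 69% |
| 20% | 58% | 74% |
| Break-even (31% / 23%) | 64% | 75% |
| 40% | 69% | 83% |

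A shorter list costs less. At n=20, one, two or three extras that explain nothing give 61%, 59% and 56%. If they explain 10% of the remainder, one gives about 65% and two about 63%.

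**5. Against the text.** The 51% and 65% figures need all five covariates in the primary model and none of them prognostic. The document fixes neither. Its precision sentence offers the baseline outcome as its only example, and it stands in a paragraph on correlations among outcome changes and exploratory models, apart from the power calculation.

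**The case for a change.** The best case for a change is that the phase list links the five variables to the arm comparison, and nothing in the document suggests they would clear a 31% or 23% bar. Eligibility narrows age to 60–80 and BMI to 28–40, which limits what either can explain. BMI probably overlaps with baseline MSSc, which already contains waist circumference. A possible loss of 13 points of power is large for a trial of 20 completers. Naming arm plus baseline MSSc as the primary model, with the fuller set as a sensitivity analysis, would take a few sentences. The generalizability aim could move to the exploratory work already foreseen: "This rich database can be used for exploratory analyses, including mediation, moderation, and mechanism".

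Part of this stands. The arithmetic is right, the precision sentence is too broad for the full set, and the primary model is not written out term by term. The eligibility and overlap arguments are plausible inference, but they do not measure prognostic strength, and if the extras are strongly prognostic the leaner model gives up power. The leaner model would also leave chance imbalance in age, sex or disease activity, which is likely enough with 13 per arm, to a secondary analysis.

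Timing weighs against a change as well. The April 2023 amendment note says enrolment had closed, and the document is dated 01/18/2024. If the list has already been fixed as promised, replacing the primary model now would override a prespecified choice and could look data-driven.

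**Conclusion.** No change is needed. The thresholds hold: with 1:1 allocation and one term each, five covariates added to baseline MSSc improve precision only if they explain more than about 31% (n=20) or 23% (n=26, upper bound) of the remaining variance. Whether they would is not knowable from the documents. With an assumed baseline R-squared of 20%, and extras explaining between none and 40% of the remainder, the effect on power runs from a loss of about 13 points to a gain of about 5 at n=20, and from a loss of about 10 to a gain of about 8 at n=26.

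This is a choice between two unbiased analyses on which experienced statisticians differ. The remaining gap is the exact set of terms in the primary model. The plan already undertakes to settle that before any analysis, and this is the safeguard against data-driven selection. An analyst fixing the list can weigh the number of terms against 20 to 26 participants without an amendment.

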Protocol Deviation/Violation: An inadvertent act (from the perspective of the PI and study staff) in which the protocol is not followed. An example of a protocol deviation is, an accidental misread of a laboratory value as being within the reference range when it actually is sufficiently abnormal to preclude study participation by the subject. A protocol violation is an intentional act (from the perspective of the PI and study staff) in which the protocol is not followed.

The NIAMS reporting requirements for Adverse Events (AEs), Serious Adverse Events (SAEs), Unanticipated Problems (UPs) and Protocol Deviations, as indicated below:

All non-serious AEs will be reported in aggregate to the Internal SO and the NIAMS (through the NIAMS Executive Secretary) as part of the routine safety report.

All SAEs (regardless of related ness or expectedness) will be reported to the NIAMS (through the NIAMS Executive Secretary) and Internal SO within 48 hours of the PI becoming aware of the event.

All UPS determined by the PI to be a non-serious AE will be reported in aggregate to the Internal SO and the NIAMS (through the NIAMS Executive Secretary) as part of the routine safety report. Those UPS determined by the PI to be an SAE will be reported to the NIAMS (through the NIAMS Executive Secretary) and the Internal SO within 48 hours of the investigator becoming aware of the event.

Protocol deviations impacting participant safety will be reported to the NIAMS (through the NIAMS Executive Secretary) and Internal SO within 48 hours of the PI becoming aware of the event; all other deviations that do not impact participant safety will be reported as part of the routine biannual safety report.

All reportable AEs will be submitted per the following DUHS IRB policies below:

An Adverse Event must be reported to the IRB if it: (i) is more likely than not related to study activities; and (ii) represents a new risk; and (iii) is unanticipated. In addition, an expected event that is occurring at a frequency or intensity greater than originally anticipated must be reported within ten business days of the investigator becoming aware of the event, study personnel will send to the IRB a Safety Event submission in iRIS.

For a reportable Serious Adverse Event, study personnel will notify the IRB within five business days of the investigator becoming aware of the event. Study personnel will send a Safety Event submission in iRIS.

For any other Unanticipated Problem or event requiring prompt reporting to the IRB, within ten business days of the investigator becoming aware of the event, study personnel will send to the IRB a Safety Event submission in iRIS.

Immediately (within 24 hours) upon learning of an unanticipated study-related death, study personnel will notify the IRB via phone or email by providing a brief summary of the event. Then within 1 week (five business days), study personnel will send to the IRB a Safety Event submission in iRIS.

A Protocol Deviation/Violation must be reported to the IRB if it: (i) affects subject rights and welfare, or (ii) affects subject safety; or (iii) affects the integrity of study data; or (iv) affects the subject's willingness to continue in the study; or (v) is specifically requested by a government agency, internal/external auditor, medical monitor, or the IRB.

Time Period and Frequency of event assessment and follow-up: The clinical course of each adverse event will be followed until resolution, stabilization, or until it has been determined that the study treatment or participation is not the cause.

How will Participants be informed: Study participants will be notified by the PI, or study team, should an AE, SAE or UP occur that impacts the following: i) affects subject rights and welfare, or (ii) affects subject safety; or (iii) affects the integrity of study data; or (iv) affects the subject's willingness to continue in the study; or (v) is specifically requested by a government agency, internal/external auditor, medical monitor, or the IRB.

Describe plans for detecting and managing incidental findings associated with study Procedures:

An incidental research finding is an abnormality discovered in the course of this research for which there is a potential health importance. During the Cardiopulmonary Exercise Test (CPX) assessment, the subject will be connected to an electrocardiogram (ECG) machine to monitor their heart rate and

rhythm. Once the CPX is complete, the ECG will be reviewed by a Cardiologist just as it would be if they were having the CPX as part of their routine medical care. There is a possibility that while reviewing the ECG, the Cardiologist may see an abnormality defined as a possible "Positive" stress test, or the presence of some other abnormal electrical conduction. This is what is called an "incidental finding." If an incidental finding occurs, the following Action Plan will be implemented:

Action Plan: We will contact the subject if the Cardiologist interprets the CPX test as "Positive". Study staff will ask the subject for their permission to give information about this incidental finding to their primary doctor and we will offer to refer them to an appropriate doctor for further evaluation. Follow-up testing will be required in order to participate in this study. The costs for any care that will be needed to diagnose or treat an incidental finding would not be paid for by this research study. These costs would be the subject's responsibility.

Clinical site monitoring will be performed utilizing an Institutional approved CQMP plan.

The trial will be conducted in compliance with the protocol, International Council for Harmonization/Good Clinical Practice requirements (ICH/GCP), and applicable state, local and federal regulatory requirements.
